1 SUMMARY

Full title	Pharmacokinetics of tranexamic acid after oral, intramuscular or intravenous administration: a prospective, randomised, cross-over pharmacokinetic study in healthy volunteers
Acronym	PharmacoTXA
Coordinating Investigator	[name]
Sponsor	London School of Hygiene & Tropical Medicine
Scientific justification	
Intravenous administration of tranexamic acid (TXA) safely reduces death due to bleeding in patients with trauma and post-partum haemorrhage (PPH) [1-3]. In both situations, most deaths occur soon after bleeding onset and treatment delay reduces the survival benefit [4]. One of the main barriers to rapid treatment is the need for an intravenous (IV) injection. Paramedics who are trained to insert intravenous lines are not always available and even when they are, securing IV access can be difficult in shocked patients with collapsed veins. Although TXA is available for oral (tablet or oral solution) and intravenous use, there has been little research into different routes of administration. Intramuscular injection would be easier and faster to administer and would require less training than IV use and the use of the oral solution may reduce the time needed to reach therapeutic levels when compared to a later IV administration. Because TXA has a wide therapeutic index, an initial IM injection could be followed by an IV TXA when this becomes possible.
 
Although the pharmacokinetics of TXA after tablet and intravenous administration have been well studied, there have been few studies of IM use or the use of oral TXA solutions. Clinical trials with tranexamic acid have shown its efficacy in several indications and reduced mortality in trauma and postpartum haemorrhage patients when administered within 3 hours [1,2,4,5]. Our hypothesis is that the pharmacokinetics of tranexamic acid after intramuscular injection or the oral solution may be suitable for early use of this molecule in emergency situations, including in remote areas around the world where a parenteral approach is not readily available or in contexts where medical personnel are not available.

Main objective and primary endpoint	
Main objective: to determine the pharmacokinetics of tranexamic acid in healthy volunteers using a population approach after oral, intramuscular or intravenous administration.
 
Primary endpoint: serum tranexamic acid concentrations versus time profiles for each administration route

Secondary objectives and endpoints	Secondary objectives: - To evaluate the local and systemic tolerance profile with the different routes of administration. - To determine the feasibility of measuring tranexamic acid in dry blood spots Secondary endpoints: - Average pain score and duration of pain after administration (visual analogue scale) for each administration route at visits V1, V3, V5 - Reaction at site of injection (redness, swelling, induration, tenderness, ecchymosis, necrosis, nerve injury, infection) for IM and IV administration route at visits V1, V2, V3, V4, V5, V6, - Vital signs (blood pressure, heart rate and respiratory rate) after administration for each administration route at visits V1, V2, V3, V4, V5, V6 - Solicited adverse events (fever, nausea, vomiting, diarrhoea, visual impairment, seizure) - Number of participants with solicited local and systemic adverse events - Number of participants reporting one or more adverse events and serious adverse events - Correlation between serum and dry blood spot concentrations for each administration route at visits V1, V3, V5
Design of the trial	Phase I/II, Single-centre, prospective, randomised, cross-over trial
Population of trial subjects	Healthy volunteers
Inclusion criteria	
 • Adult healthy volunteers both men and non-pregnant women • ≥ 18–≤ 45-year-old • Body mass index between ≥ 18 and ≤ 30 kg/m², and bodyweight between ≥ 50 and ≤ 100 kg • Coagulation test results of fibrinogen, D-dimers, prothrombin time and a partial thromboplastin time within normal limits at screening (see protocol for details) • Normal renal function based on medical history and laboratory tests (laboratory test of serum creatinine should be in the range of 0.6–1.1 mg/dL for women and 0.7–1.3 mg/dL for men. Glomerular filtration rate (GFR) should be 90 mL/min/1.73m² or greater (adjusting for age, sex, weight and ethnicity) • If a woman, must have a negative urine β-human chorionic gonadotropin (βhCG) pregnancy test at screening and inclusion visits • Provision of signed informed consent prior to any study specific procedure • People with public healthcare insurance (France)
Exclusion criteria	
 • Previous thrombotic event or pre-existing pro-thrombotic disease

	
 • Any history of seizures • Any chronic or active cardiovascular or renal disease • Planned general anaesthesia or surgery in the 3 months following inclusion • Pregnant and/or breastfeeding • Visual disturbance • Haematuria • Known allergy or contraindications to the study drugs or any of the excipients of the formulations • Use of any prescription or non-prescription medication (including hormonal contraception) within 7 days before the first dose of the study drug is scheduled • Inability to give informed consent • Previous participation during the year in clinical studies compensated for an amount incompatible with participation in this study, verified by recording in the national register of subjects participating in human research trials • Legal criteria: 
 - People deprived of liberty by judicial or administrative decision - Adult protected bylaw (France)
Investigational medicinal product(s)	
Tranexamic acid (Exacyl®), 0.5 g/5 ml, injectable solution: Each volunteer will receive one x 1g intravenous injection and one x 1g intramuscular injection.
 
Tranexamic acid (Exacyl®), 1.0 g/10 ml, oral solution: Each volunteer will receive one x 2g oral solution.

Comparator treatment	Not Applicable
Interventions added for the trial	
 - Drug administration - Blood samples for pharmacokinetic study
Risks added by the trial	
The most frequent risks associated with the administration of tranexamic acid through the intravenous, intramuscular and oral routes are digestive disorders (diarrhoea, nausea, vomiting; appearing in >1/100 and <1/10 patients); allergic dermatitis (>1/1000 and <1/100). Cases of visual impairment or convulsions have been reported with tranexamic acid, but only at high doses or during cardiac surgery. In the present study, the doses (1g through the parenteral routes and 2g through the oral route) are lower than doses used in routine clinical practice.
 
Insertion of intravenous cannula for intravenous administration of TXA and blood sampling may cause pain (common), bruising (rare), local allergic reaction secondary to disinfectant or adhesive plaster, vagal malaise and possibly infection (very rare).
 
Intramuscular injection procedure of a large volume may cause pain (common), Local reaction at site of injection (site: redness (common), swelling (common), tenderness (common),

	
ecchymosis (common), induration (rare), necrosis (very rare), nerve injury (very rare), infection (rare) and systemic events (allergic reaction (very rare), infection (very rare)).
 
One study of subfascial and intramuscular infiltration of 2g of tranexamic in 67 elderly patients having surgery for peritrochanteric fracture reported no adverse effects up to 2 weeks.
 
Since TXA is eliminated mainly in the urine, only patients with normal renal function will be included in the trial. Therefore no risk of drug accumulation is anticipated.

Scope of the trial	To determine doses and routes to be used in subsequent trials in postpartum women and patients with severe bleeding after trauma and to assess the safety of administration of tranexamic acid by intramuscular injection
Number of subjects included	30 healthy volunteers to be screened 15 healthy volunteers to be select and randomised for the pharmacological study
Number of sites	1
Duration of the trial	
 - Duration of the inclusion period: 16 months - Duration of the research period for each participant: 7 days of participation over a period of 3 months maximum - Total duration of the research period: 19 months
Number of enrolments expected per site and per month	1
Statistical analysis	Tranexamic acid time-courses will be analysed using the nonlinear mixed effect modelling software program Monolix 2019R1 version. All other data will be analysed using STATA.
Sources of funding for the trial	Funding is by the London school of Hygiene & Tropical Medicine from a grant provided to them by the Bill and Melinda Gates Foundation and Wellcome.
Trial will have a Data Monitoring Committee	No

2 SCIENTIFIC JUSTIFICATION FOR THE TRIAL

2.1 Existing knowledge relating to the condition under investigation

Tranexamic acid (TXA) reduces bleeding by inhibiting the enzymatic breakdown of fibrin blood clots (fibrinolysis) [6]. Plasminogen produced by the liver is converted into the fibrinolytic enzyme plasmin by tissue plasminogen activator (tPA). Plasminogen and tPA bind to c-terminal lysine residues on fibrin leading to localised plasmin formation and fibrin cleavage [7]. TXA is a molecular analogue of lysine that inhibits fibrinolysis by competing with fibrin for the lysine binding sites in plasminogen. TXA inhibits the capacity of plasminogen and plasmin to bind to fibrin, hence preserving blood clots from plasmin-mediated lysis [6].

Intravenous administration of TXA safely reduces death due to bleeding in patients with trauma and post-partum haemorrhage (PPH) [1-3]. In both situations, most deaths occur soon after bleeding onset and treatment delay reduces the survival benefit [4]. One of the main barriers to rapid treatment is the need for an intravenous (IV) injection. Paramedics who are trained to insert intravenous lines are not always available and even when they are, securing IV access can be difficult in shocked patients with collapsed veins. Although TXA is available for oral (tablet or oral solution) and intravenous use, there has been little research into different routes of administration. Intramuscular injection would be easier and faster to administer and would require less training than IV use and the use of the oral solution may reduce the time needed to reach therapeutic levels when compared to a later IV administration. Because TXA has a wide therapeutic index, an initial IM injection or oral administration could be followed by an IV TXA when this becomes possible.

2.2 Summary of relevant pre-clinical and clinical trials

Although the pharmacokinetics of TXA after tablet and intravenous administration have been well studied, there have been few studies of IM use or of the use of oral TXA solutions. A systematic search identified two pharmacokinetic studies of IM TXA conducted in 1975 and 1986 that included six (male) participants [8,9]. These showed that the bioavailability of TXA after IM injection is over 95% with therapeutic TXA levels (>10 mg/L) achieved within 30 minutes of administration, but there was a wide variability between the two studies, with T_{max}

around 0.5 or 1 hr, and C_{max} of approximately 20 or 12 $\mu\text{g/ml}$ for the same 500 mg dose. A individual-patient data metanalysis confirming this excellent intramuscular bioavailability was recently published by our team [10].

One study of subfascial and intramuscular infiltration of 2g of TXA in 67 elderly patients having surgery for peritrochanteric fracture reported no adverse effects up to 2 weeks. However, this study did not report on the bioavailability of intramuscular TXA [11].

Larger well-designed studies with a greater sample-size would be helpful to better describe the pharmacokinetics through the IM route and to confirm the bioavailability, which would suggest that IM may be a feasible alternative to IV use when IV administration is either impractical or would result in treatment delay. We will examine the pharmacokinetics of TXA after IM injection and after use of an oral TXA solution.

With respect to safety in healthy volunteers, TXA (1g IV) was previously administered to 49 healthy volunteers treated with rivaroxaban in a study aimed at assessing the effects of 4-factor prothrombin complex concentrate and tranexamic acid on bleeding parameters and pharmacodynamics after a punch biopsy procedure (NCT02561923). No serious adverse events were reported in this study and none of the subjects withdrew from the study due to adverse events. No clinically relevant laboratory changes, vital signs abnormalities, physical examination abnormalities, or ECG abnormalities were reported during the study [12]. The pharmacokinetics of TXA was also reported in 6 previous studies in healthy volunteers with doses ranging from 0.5 to 2 g, including 2 studies with an intramuscular administration, with no specific report of adverse events [8,9,13-16].

Ethnic origin is known to have an impact on the glomerular filtration rate, which should modify the drug pharmacokinetics, especially for tranexamic acid due to its 100% kidney elimination. Hence, nonblack ethnicity is an independent factor associated with a lower glomerular filtration rate [17].

TXA has been in clinical use for over 40 years for a variety of clinical conditions where there is haemorrhage or a risk of haemorrhage. Both intravenous and oral routes (tablets and solution)

have marketed authorisation in France. In summary, clinical trials of TXA has been carried out in the following bleeding conditions:

Obstetric haemorrhage:

Treatment of postpartum haemorrhage: A systematic review identified two trials involving 20,212 women and showed that 1 gram of intravenous TXA (plus an additional 1 gram if bleeding continued up to 24 hours) reduces the risk of death due to bleeding after postpartum haemorrhage (PPH) compared to placebo. There is no evidence for an increase in risk of thromboembolic events, seizures or any other side effects associated with TXA [18]. Based on this evidence, the WHO recommends the early use of TXA (within 3 hours of birth) in women with PPH [19].

Prevention of postpartum haemorrhage: A systematic review including 26 randomised trial of TXA for the prevention of PPH found that most trials are small and unreliable [20]. One exception is the placebo-controlled TRAAP trial which enrolled 4079 women who were giving birth vaginally in French hospitals [21]. There was no statistically significant difference in the primary outcome of blood loss ≥ 500 mL. Fewer woman in the TXA group received additional uterotonics and fewer experienced clinically significant PPH according to care provider. The rates of nausea and vomiting were higher in the TXA group compared to the placebo group.

Traumatic haemorrhage:

The CRASH-2 trial involving 20,211 trauma patients found that TXA reduced the risk of death from bleeding by 15% compared to placebo. The trial also found that early administration of TXA in trauma patients (≤ 3 hr) was more effective in reducing deaths from bleeding than late administration (>3 hr). There was no evidence for an increase in risk of thromboembolic events, seizures or any other side effects associated with TXA [3].

Gastrointestinal bleeding

A systematic review including eight randomised trials found that patients with acute upper gastrointestinal bleeding may benefit from the administration of TXA [22].

Two small trials have assessed the effect of oral TXA in patients with lower gastrointestinal bleeding. In one trial the proportion of stools containing visible blood was lower when patients received TXA [23]. However, in the second trial there were no statistically significant differences between the TXA and placebo groups for any of the outcomes assessed [24].

Surgical haemorrhage

A systematic review of 129 randomised trials found that TXA reduced the risk of receiving a blood transfusion by 38% and the amount of blood loss by 34% in patients undergoing surgery. The effect of TXA on risk of thromboembolic events was uncertain [25].

Intracranial haemorrhage

Spontaneous intracerebral haemorrhage: A systematic review including nine randomised controlled trials suggest that TXA reduces the risk of rebleeding. However, long term use of TXA may increase the risk of cerebral ischaemia in these patients. There is some evidence that shorter treatment might reduce rebleeding without an increase in the risk of ischaemia [26].

A trial of TXA in patients with spontaneous intracerebral haemorrhage observed no statistically significant differences in functional status or death at day 90. There were fewer deaths at day 7 in the TXA group [27].

Traumatic brain injury: The results of two randomised trials in patients with traumatic brain injury showed that TXA reduced intracranial haemorrhage growth compared to placebo. However, the effect of TXA on risk of death and thromboembolic events is uncertain [28-30].

Pulmonary haemorrhage

A systematic review including two small randomised trials found that TXA reduced the amount and duration of blood loss in patients with haemoptysis [31]. Another recent trial also suggests that using inhaled TXA can be safe and effective to control bleeding in patients with non-massive hemoptysis [32].

Menorrhagia

Randomised trials of oral TXA show that TXA reduces blood loss and improves indicators of quality of life in women with menorrhagia [33].

Ocular haemorrhage

Randomised trials of oral TXA shows that it reduces the risk of secondary haemorrhage in patients with hyphema [34].

Topical use of tranexamic acid

One concern with administering TXA intramuscularly is local tissue reaction. The evidence from a systematic review which investigated the efficacy and safety of topically applied tranexamic acid in major surgery (where the drug is applied directly into joints, surgical wounds and body organs) identified 67 studies involving 6,034 patients. There were no major differences between topical and intravenous tranexamic acid with respect to safety [35].

2.3 Hypothesis for the trial

Clinical trials with tranexamic acid have shown its efficacy in several indications and reduced mortality in trauma and postpartum haemorrhage patients when administered within 3 hours [1,2,4,5]. Our hypothesis is that the pharmacokinetics of tranexamic acid after intramuscular injection or the oral solution may be suitable for early use of this molecule in emergency situations, including in remote areas around the world where a parenteral approach is not readily available or in contexts where medical personnel are not available.

2.4 Description of the population of trial subjects and justification for the choice of subjects

Fifteen healthy volunteers will be included in an age range compatible with motherhood for women. This study in healthy volunteers will allow a description of the drug pharmacokinetics and a comparison of the three different administration routes in people without any specific medical condition. Subsequent trials will be planned in specific populations such as trauma patients or postpartum women. For these reasons, we will include in the present study both men and women, in an age range compatible with motherhood for women.

2.5 Name and description of the investigational medicinal product(s)

Patient will receive the marketed forms of tranexamic acid:

- Exacyl® (Sanofi Aventis) 0.5 g/5 ml injectable solution
- Exacyl® (Sanofi Aventis) 1 g/10 ml oral solution.

See Section 7 for further information about the product.

2.6 Description and justification of the dosage, route of administration, administration schedule and treatment duration

Each volunteer will receive one dose of medication through each of the three routes (oral, intravenous, intramuscular), on three separate days. The selected doses are 1g for the intravenous and intramuscular routes and 2g for the oral route due to the 100% intramuscular bioavailability and 50% oral bioavailability [10].

See Section 7 for further information about the administration of the product.

2.7 Summary of the known and foreseeable benefits and risks for the study participants

There is no benefit for participants. The foreseeable risks are those related to IMP and the routes of administration. The most frequent risks associated with the administration of tranexamic acid through the intravenous, intramuscular and oral routes are:

- digestive disorders (diarrhoea, nausea, vomiting; appearing in >1/100 and <1/10 patients)
- allergic dermatitis (>1/1000 and <1/100)

Cases of visual impairment or convulsions have been reported with tranexamic acid, but only at high doses or during cardiac surgery. In the present study, the doses (1g through the parenteral routes and 2g through the oral route) are lower than doses used in routine clinical practice.

Insertion of intravenous cannula for intravenous administration of TXA and blood sampling may cause pain (common), bruising (rare), local allergic reaction secondary to disinfectant or adhesive plaster, vagal malaise and possibly infection (very rare).

Intramuscular injection procedure of a large volume may cause pain (common), Local reaction at site of injection (including Injection site redness (common), Injection site swelling (common), Injection site tenderness (common), Injection site ecchymosis (common), Injection site induration (rare), injection site necrosis (very rare), injection site nerve injury

(very rare), injection site infection (rare) and systemic events (allergic reaction (very rare), infection (very rare)). One study of subfascial and intramuscular infiltration of 2g of tranexamic acid in 67 elderly patients having surgery for peritrochanteric fracture reported no adverse effects up to 2 weeks [11]. One concern with administering TXA intramuscularly is local tissue reaction. The evidence from a systematic review which investigated the efficacy and safety of topically applied tranexamic acid in major surgery (where the drug is applied directly into joints, surgical wounds and body organs) identified 67 studies involving 6,034 patients. There were no major differences between topical and intravenous tranexamic acid with respect to safety [35].

Since TXA is eliminated mainly in the urine, only participants with normal renal function will be included in the trial. Normal renal function is defined as a laboratory test of serum creatinine in the range of 0.6–1.1 mg/dL for women and 0.7–1.3 mg/dL for men and a glomerular filtration rate (GFR) of 90 mL/min/1.73m² or greater (adjusting for age, sex, weight and ethnicity). Therefore no risk of drug accumulation is anticipated.

3 OBJECTIVES

3.1 Primary objective

- To determine the pharmacokinetics of tranexamic acid in healthy volunteers using a population approach after oral, intramuscular or intravenous administration

3.2 Secondary objectives

- To evaluate the local and systemic safety profile with the different routes of administration.
- To determine the feasibility of measuring tranexamic acid in dry blood spots

4 DESCRIPTION OF THE TRIAL

4.1 Concise description of the primary and secondary endpoints

4.1.1 Primary endpoint

- Serum tranexamic acid concentrations versus time profiles for each route of administration.

4.1.2 Secondary endpoints

- Average pain score and duration of pain after administration (visual analogue scale) for each administration route at visits V1, V3, V5
- Reaction at site of injection (redness, swelling, induration, tenderness, ecchymosis, necrosis, nerve injury, infection) for IM and IV administration route at visits V1, V2, V3, V4, V5, V6,
- Vital signs (blood pressure, heart rate and respiratory rate) after administration for each administration route at visits V1, V2, V3, V4, V5, V6
- Solicited adverse events (fever, nausea, vomiting, diarrhoea, visual impairment, seizure)
- Number of participants with solicited local and systemic adverse events
- Number of participants reporting one or more adverse events and serious adverse events
- Correlation between serum and dry blood spot concentrations for each administration route at visits V1, V3, V5

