4.2 Research methodology

4.2.1 Design of the trial

This research study is a phase I/II, single-centre, prospective, randomised, cross-over trial in healthy volunteers.

The design will be as follows:

The volunteers will be randomized into each of the 6 treatment groups (2-3 patients per group). The volunteers will receive tranexamic acid through the intravenous, intramuscular or oral route, in 6 different orders depending of the group, on three separate days (see Figure 1). The order used for the different routes of administration in each volunteer is not a factor that could influence the results of this pharmacokinetic study. Nevertheless, in order to reflect the best of all the variability that could be introduced into the system, the design selected for the study includes the 6 possible groups with regard to the sequence of routes of administration. Since the planned number of volunteers is 15, the groups consist of 2 or 3 volunteers alternately. This will not affect the final analysis, since the different groups will not be compared with each other, only the 3 routes of administration (oral, intravenous and

intramuscular) will be compared, each with a total of 15 patients. Any randomized participant who has not received all three drug doses will be replaced and the replacement will be allocated to the same randomisation group.

[figure not shown]

Figure 1: *Overview of randomisation groups*

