5.2 Inclusion visit (V1)

All **inclusion and exclusion criteria** have to be checked by physician, to ensure laboratory tests done at the screening visit are within normal values and for women, the pregnancy test is negative.

If a volunteer meets all inclusion and has no exclusion criteria and s/he consents to participate, the participant is considered **enrolled**. The investigator will randomize her/him to one of six groups (see Section 4.2.1).

Visit V1 (=1st drug administration):

- All women must have a **pregnancy test** (urine β hCG) done which must be negative to continue this visit.
- Participants medical history will be checked to ensure there are no changes since V0 visit.
- Baseline blood pressure, heart rate and respiratory rate will be recorded
- T₋₁: One blood sample will be taken for pharmacokinetics immediately prior to drug administration (0,5 mL venous blood taken in a dry tube without anti-coagulant)

- T₀: Drug Administration (PO, IV or IM) (as per randomization)
- **Pain assessment** using a Visual Analogue Scale (VAS) will be recorded immediately after drug administration and at 2 hourly intervals up to 8 hours. The VAS used will be the Numerical Pain Rating Scale where individuals rate their pain on a ten-point numerical scale. The scale is composed of 0 (no pain at all) to 9 (worst imaginable pain). The duration of any pain associated with IV or IM administration will be assessed once at 8 hours. Participants will be offered pain relief if needed in the form of simple analgesia (paracetamol).
The duration of any pain associated with IV or IM administration will be assessed once at 8 hours.
- Blood samples for **pharmacokinetics** (*0,5 mL of venous blood in dry tube without anti-coagulant*) will be taken at the following times after drug administration:
 - T₀+ 5min (only for IV route)
 - T₀+30min
 - T₀+1h
 - T₀+2h
 - T₀+3h
 - T₀+4h
 - T₀+5h
 - T₀+6h
 - T₀+8h (only for IM and PO routes)
- **Dry Blood Spot:** At one time-point (any time-point between T₀+ 5min and T₀+8h), a capillary blood sample will be taken at a finger with a lancet and a drop of blood will be placed on Mitra[®] device. An aliquot of 200µL of whole blood will be taken and aliquoted from the venous blood sample taken at the same time.

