5.4 End of study visit

Due to the low toxicity of the molecule and its half-life ranging from 1 to 10 hours (depending on patient populations), healthy volunteers who participated in the study and received at least one administration of tranexamic acid will have a telephone follow-up after the end of the study. They will be contacted by **telephone 48 hours after the last administration** to check for any adverse events.

5.5 Expected length of participation, chronology and duration of the study.

Maximum period between screening and enrolment	7 days
Inclusion period	16 months
Duration of participation for each participant	Screen + 3x 2 days + 1 phone contact = over 3 months
Total study period	19 months

Table summarising the chronology of the study

Action	Visit V0 Screening	Visit V1 Inclusion	Visit V2 V1+24h	Visit V3	Visit V4 V3+24h	Visit V5	Visit V6 V5+24h	End of Study
Verification of Eligibility Criteria	X	X						
Signature of Informed Consent	X							
Demographic data	X							
Medical History	X							
Physical Examination, including weight and height	X							
Vital signs (including Blood pressure, heart rate, respiratory rate)	x	x	x	x	x	x	x	
Randomisation		x						
Drug Administration (PO, IM or IV)		X		X		X		
Pain (Visual Analogue Scale and duration of pain)		X	X	X	X	X	X	
Reaction at injection sites		X	X	X	X	X	X	
Laboratory Tests	X	X		X		X	X	
Haematology tests (full blood count)	x						x	
Renal function test (urea, creatinine, GFR)	x						x	
Coagulation tests (fibrinogen, D-dimers, prothrombin time and partial thromboplastin time)	x						x	
For women: pregnancy test (urine β hCG)	x	x		x		x	x	
Pharmacokinetic		X	X	X	X	X	X	
1 sample immediately prior to drug administration		x		x		x		
8 samples from T0+5min to T0+8h		x		x		x		
1 sample at T0+24h			x		x		x	
Dry Blood Spot: 1 capillary sample at any time-point between T0+5min and T0+8h and one 200 μ L whole blood aliquot of the venous sample taken at the same time		X		X		X		
Concomitant treatments	X	X	X	X	X	X	X	
Adverse Event		X	X	X	X	X	X	X
Telephone Follow-Up								X

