5.7 Biological samples

5.8.1 Pharmacokinetics study

Serum PK samples: each dosage requires 0,5 ml of blood in dry tube without anticoagulant. The PK sample will then be centrifuged for 10 min at 4 000 rpm then the serum will be frozen at -20°C

The samples will be kept frozen at -20°C in the Clinical Investigation Centre of Necker Hospital. Once all the samples have been collected, they will be sent frozen to the mass spectrometry platform of the UFR Sciences de la Santé Simone Veil, University Versailles Saint Quentin, [name], France to perform the analysis under the supervision of [name].

Dry Blood Spot: for each participant, at visit 1, 3 and 5, at one time-point (any time-point between T0+ 5min and T0+8h), a capillary blood sample will be taken at a finger with a lancet and a drop of blood will be placed on Mitra® device. An aliquot of 200µL of whole blood will be taken and aliquoted from the venous blood sample taken at the same time. The filter papers will be kept at ambient temperature in the Clinical Investigation Centre of Necker Hospital during the study period. Once all the samples have been collected, they will be sent in the same time than serum PK samples to the UFR Sciences de la Santé Simone Veil, University Versailles Saint Quentin.

The inclusion number will be used to identify the sample, no identifying data will be transferred to the laboratory.

Once all analysis for this trial has been completed, all blood samples will be destroyed.

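### Correlation with serum, at spot times left open, cannot show whether dry blood spot values can stand in for serum values; the 45 planned pairs could, and the paired sample volumes need reconciling

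*Protocol*

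**What the plan says.** Protocol section 3.2 sets the secondary objective: "To determine the feasibility of measuring tranexamic acid in dry blood spots". The only endpoint that serves it, in section 4.1.2, is "Correlation between serum and dry blood spot concentrations for each administration route at visits V1, V3, V5".

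The spot time is left open. The subsection on the pharmacokinetics study within section 5.7 says that "at one time-point (any time-point between T0+ 5min and T0+8h), a capillary blood sample will be taken at a finger", and the chronology table in section 5.5 repeats it: "1 capillary sample at any time-point between T0+5min and T0+8h". The visit descriptions in sections 5.2 and 5.3 say the same, and none gives a rule for allocating times. The serum schedules differ by route: the 5-minute sample is for IV only and the 8-hour sample for IM and oral only.

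On volume, the section 5.7 subsection says that "each dosage requires 0,5 ml of blood in dry tube without anticoagulant", and sections 5.2 and 5.3 specify 0.5 mL for each venous sample. Section 5.2 then adds, for the spot: "An aliquot of 200µL of whole blood will be taken and aliquoted from the venous blood sample taken at the same time". No larger draw is stated for that time-point.

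Section 4.2.1 says that the three routes "will be compared, each with a total of 15 patients".

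**The concern.** A spot method is useful if its reading can replace the serum concentration or be converted to it. That requires knowing how far the spot reads from serum on average, how much individual pairs scatter, and whether either changes with concentration. Correlation answers none of these. It measures how closely the pairs follow a straight line, relative to the range of concentrations sampled. That range is set by the sampling times, which the protocol leaves to whoever takes the spot. The same assay could therefore look strong or mediocre for reasons unrelated to its quality, and a badly calibrated one could look excellent.

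The volume statements raise a second, separate question. Each serum value in the spot comparison comes from a sample that has given up part of the volume the protocol says an assay needs, and those serum values also belong to the primary endpoint.

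**Working it through.** **The plan's own figure.** The only design figure is N = 15 (section 12.2), justified by relative standard errors below 30% for the pharmacokinetic parameters. Its input parameters are not in the protocol, so it cannot be reproduced. It is not tied to the spot comparison.

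**Counts.** Pairs: 15 participants × 3 visits = 45, or 15 per route. Serum samples: (1 pre-dose + 8 + 1 at 24 h) × 3 routes × 15 = 450.

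**Bias.** For any constant a and any b > 0, corr(x, a + b·y) = corr(x, y). A constant or proportional error in the spot therefore leaves r unchanged. A simulation shows the practical effect. It assumed 15 pairs, mono-exponential decline with a half-life of 1 to 3 h, between-subject log-SD 0.2, within-pair CV 15%, and times drawn from 5 min to 6 h.

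| | Median r | Median concordance coefficient |
|---|---|---|
| Spots unbiased | 0.95–0.99 | 0.94–0.98 |
| Spots 40% low | 0.95–0.99 | 0.57–0.78 |

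With all pairs at one time and no bias, median r fell to about 0.81.

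**Dependence on timing.** If both methods have independent log-scale error e, and true concentrations have log-SD s, then r = s²/(s² + e²). Take e = 0.15 (assumed):
- one common time, s = 0.25 (assumed): 0.0625/0.0850 = 0.74
- spread, s = 0.5 (assumed): 0.25/0.2725 = 0.92
- spread, s = 1.0 (assumed): 1/1.0225 = 0.98

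The spread values can be checked against the IV times (5 min, 0.5, 1, 2, 3, 4, 5 and 6 h), whose SD is 2.03 h. With s² = (2.03 × ln 2 / half-life)² + 0.25², a half-life of 3 h gives s = 0.53 and one of 1.5 h gives 0.97. Section 5.4 quotes half-lives of 1 to 10 h across patient populations. At 10 h, s would be only 0.29 and r 0.79, so the contrast shrinks as elimination slows.

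**Precision of r.** By Fisher's z, an observed r of 0.95 has a 95% CI of 0.85 to 0.98 with 15 pairs and 0.91 to 0.97 with 45.

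**What the same pairs could give.** On the log scale, with within-pair SD σ, the mean ratio has a 95% CI of ×/÷ exp(t·σ/√n). For an assumed within-pair CV of 10 to 30%:
- n = 15: a factor of 1.06 to 1.18
- n = 45, treated as independent: a factor of 1.03 to 1.09

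Each participant contributes three pairs, so the pooled precision lies between these. At a CV of 15% the limits of agreement are 0.75 to 1.34 around the mean ratio. The upper limit has a 95% CI of 1.16 to 1.55 (n = 15) or 1.24 to 1.45 (n = 45).

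**Volume.** 0.5 − 0.2 = 0.3 mL, which is 60% of the stated requirement. This applies to 45 of 450 samples (10%) and to all 45 comparators. With an assumed haematocrit of 0.36 to 0.50, the maximum serum yield, volume × (1 − haematocrit), falls from 0.25–0.32 mL to 0.15–0.19 mL.

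**The case against.** The stated objective is feasibility, not agreement, and the protocol sets no threshold on r. No rule exists by which a biased method would be declared feasible or a sound one rejected. That is correct, and agreement is a standard brought by the review. But a correlation without a criterion does not settle feasibility either. The statistical analysis plan, not shown here, may add agreement statistics, and the endpoint wording does not exclude them. It could not repair the choice of spot times once samples are collected.

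Reporting by route is defensible. The IV dose is 10 mL at about 1 mL/min (section 7.1.1), roughly 10 minutes. If T0 is the start of infusion, a 5-minute spot falls during drug input, and capillary-venous differences could then depend on route. Pooled results should therefore be accompanied by results by route.

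The 0.74 needs every spot at one time, which nothing in the protocol suggests. It marks the low end of what the wording permits.

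Stronger readings are tempting, and the documents do not support them:
- A reader might infer that agreement cannot be shown. Every spot has a simultaneous serum value, so the limit lies in the chosen endpoint, not in the data.
- A reader might infer that the serum comparator is compromised. The 0.5 mL is a blood volume, the serum the assay consumes is not stated, and a smaller volume does not by itself bias a concentration.
- A reader might infer that a tube without anticoagulant is wrong for the whole-blood aliquot. The protocol does not say when the aliquot is taken or into what container, nor what it is for.

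**Conclusion.** The concern holds for the endpoint and the sampling rule. As worded, the endpoint cannot reveal constant or proportional bias: a 40% shortfall leaves r at 0.95 to 0.99 in the simulated spread-time case. Its size varies with unallocated times, from about 0.74 at one time to 0.92–0.98 when spread. These values rest on 15% error per method and log-SDs of 0.25 versus 0.5–1.0, none of which is in the protocol; a long half-life would narrow the gap. The planned pairs can support a usable agreement estimate, so the weakness is cheap to remedy.

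The volume point is an unreconciled pair of statements affecting 45 of 450 samples. It is not evidence of biased serum values, and no effect on the primary pharmacokinetic result is shown. Since the objective is secondary, this is an improvement that should be made rather than a threat to the trial.

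**What to change.** - **Endpoint.** Keep the correlation as descriptive. Name as the stated measure the geometric mean spot/serum ratio with its 95% CI, together with limits of agreement on the log scale. Estimate both from a mixed model with a random participant effect, pooled over routes and also shown by route. Check the ratio against concentration.
- **Spot times.** Pre-assign them so that each route's own sampling schedule is covered, with 5 minutes used for IV only and 8 hours for IM and oral only.
- **Volume.** Either state the minimum volume the assay needs and confirm that 0.3 mL of blood supplies it, or draw the 0.2 mL in addition to the 0.5 mL.

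The cost is revised endpoint wording, a list of times and, if the extra draw is chosen, 3 × 0.2 = 0.6 mL more blood per participant. No additional participants or spots are needed.
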